6.3 Waiver or alteration of authorization statements of agreement

Protected health information obtained as part of this research will not be reused or disclosed to any other person or entity, except as required by law, for authorized oversight of the research study, or for other permitted uses and disclosures according to federal regulations.

The research team will collect only information essential to the study and in accord with the 'Minimum Necessary' standard (information reasonably necessary to accomplish the objectives of the research) per federal regulations.

Access to the information will be limited, to the greatest extent possible, within the research team. All disclosures or releases of identifiable information granted under this waiver will be accounted for and documented.

7.0 Study Design and Procedures

7.1 Study Design

Phase II randomized controlled trial, computer generated randomization. Investigators were blinded to randomization generation.

7.2 Study Procedures

7.2.1 Clinical covariates:

Detailed clinical covariates will be obtained (following consent at the participant's first hematology/oncology appointment) from questionnaires and medical record review including demographics (age, gender, race), cardiovascular history and risk factors (hypertension, arrhythmia, hyperlipidemia, tobacco use, family history of cardiac disease), clinical variables (blood pressure, weight), treatment regimen (ACT, TAC, CAF), and medication use.

7.2.2 Blood sampling:

Blood sampling for research purposes will occur in conjunction with clinical blood draws or prior to chemotherapy infusion to limit inconvenience to the research subjects. Approximately 16 ml of blood will be obtained during a clinical blood draw prior to initiation of cancer therapy and 16 ml following completion of anthracycline dosing (HER2- patients receiving ACT) or at cycle 3 (HER2+ patients receiving TCH+pertuzumab), as well as 16 ml following completion of

chemotherapy (two 8ml tubes – (1) EDTA and (1) Serum). Plasma, serum, and buffy coat (if applicable) will be aliquotted and stored. All spinning, aliquotting, and storage will occur in the Clinical Research Biospecimen Core Lab (C6529) or in the PI's lab. Blood sampling will be done in the usual fashion with standard phlebotomy precautions. EDTA plasma will be used to assess metabolomics and cytokines. One ml of serum will be used for a chemokine multiplex panel. If consented to by the participant, 1ml off serum or plasma will be used to evaluate level of cell-free DNA (tumor DNA). Buffy coat will be used to assess epigenetic changes in immune cells (white blood cells) or somatic DNA.

7.2.3 Transthoracic echocardiogram:

Resting echocardiograms with conventional measures of systolic and diastolic function, as well as measures of strain and strain rate will be obtained at baseline and following chemotherapy. Conventional resting echocardiograms are obtained clinically before chemotherapy (as well as during and after neoadjuvant chemotherapy for HER2+ patients). Resting echocardiograms are not obtained clinically following chemotherapy for HER2- patients; therefore this measurement is additional for research. There will be no additional costs to the patient for any of these echocardiograms. Echocardiograms that are performed as part of clinical care will be read in the conventional manner and reported in the subject's medical record as per routine care. For patients receiving a follow up research echocardiogram we will call the patient to share clinically relevant results.

7.2.4 Maximal oxygen consumption (VO₂) test:

All subjects will undergo a treadmill exercise test to estimate maximal oxygen consumption (VO₂max) as an index of cardiopulmonary fitness. Prior to beginning the test, electrodes will be positioned on the subject's torso in order to acquire a 12-lead ECG and heart rate. Resting ECG, heart rate, and BP will be obtained prior to beginning the test, during each stage of the test, and for 5 minutes after the test is stopped (recovery period). Subjects will begin an incremental treadmill protocol with a change in workload (speed and/or grade) every 3 minutes (Modified Bruce Protocol). At each stage of the test, subjects will indicate their Rating of Perceived Exertion (RPE) using a Borg category-ratio scale. The workload will be increased until subjects reach 80% of their age-predicted HRmax. During this test, VO₂ will be measured by open circuit spirometry. Subjects will wear a nose clip and breathe through a mouthpiece to collect expired air. Ventilation, CO₂ production, and the respiratory exchange ratio (RER; expired VCO₂/VO₂ consumed) will be continuously measured. When the test ends, the treadmill grade will be decreased to 0% while the subject continues to walk slowly for several minutes. The subject will then be seated in a chair for the remaining recovery period. ECG, heart rate, and BP will continue to be monitored until heart rate decreases to within 10 beats/min of their resting heart rate. VO₂ measurements and HR response to the protocol will be used to predict VO₂max. If, during the baseline exercise test we have to terminate the test for an absolute indication (other than participant's request to stop/volitional fatigue) we will recommend to the participant that they contact a medical provider (primary care physician/cardiologist) to follow up on our observations.

7.2.5 Aerobic exercise training intervention:

All participants randomized to the intervention group will be asked to keep an exercise log with the date, time, average heart rate obtained from a heart rate monitor, duration of workout and stretching, and any comments regarding the workout. Participants will be instructed to bring workout logs to infusion sessions for review. Participants will also wear a Polar Heart Rate monitor (US model RS400, Polar Electro Inc., Lake Success, NY) during exercise to monitor exercise intensity. The heart rate monitors will be brought back to the Medical Center at infusion sessions in order for the staff to objectively monitor exercise adherence. A member of the research team will collect data at these infusion sessions (exercise logs and watch). A

second watch, stripped of any participant data, is given back to participants to continue exercise training.

The aerobic exercise intervention will work toward the target of 75 minutes of aerobic exercise per week at 60%-85% of baseline VO₂max. Walking has been chosen because it is the preferred mode of exercise training for breast cancer patients. (34)

In Weeks 1-4 (Introductory Phase) of the program, the frequency, duration, and intensity of aerobic exercise will be progressively increased from an initial prescription of 3 session/wk for ~20 mins/session at ~60% of VO₂max to ~25 mins/session at ~65% of VO₂max at the end of week 4. The goal of these sessions will be to introduce aerobic exercise, including warm-up as well as walking pace and proper form.

In Weeks 5 to 11 (Intermediate Phase), the goal will be to introduce higher intensity aerobic exercise. Specifically, aerobic exercise intensity will range between ~60%-70% VO₂max for two sessions per week; in the remaining session, aerobic exercise intensity will be set at ventilatory threshold (~75% VO₂max).

In Weeks 12 to 24 (Maintenance Phase) participants will be asked to perform 3 aerobic exercise sessions per week at ~60%-75% VO₂max with sessions ≥25 minutes in duration with the intensity of the once per week harder sessions ≥80% VO₂max.

An exercise physiologist will contact the participants weekly via phone or in person during their infusion visit to troubleshoot and provide support.

7.2.6 Control group activities:

Participants randomized into the control group were asked to maintain their usual level of physical activity and to not engage in any new exercise program during study participation. Participants in the control group will be contact at each infusion session and asked about their experience and well-being during treatment (i.e. attention control). Participants in the control group will have DVDs and an exercise binder shipped to their house following: completion of all study visits (including their exercise safety education session), and clearance from surgical oncology.

7.2.7 Quality of life surveys:

Physical Activity Questionnaire, Work Productivity and Activity Impairment Questionnaire (WPAI), EuroQol 5D (EQ-5D), Medical Outcomes Study 36-Item Short Form (SF-36), Fatigue Symptom Inventory (FSI), short form, and the Adverse Effects survey. These will be administered during the first chemotherapy infusion session, a midpoint chemotherapy session (defined above for blood draws), and at the last neoadjuvant chemotherapy session. The Injury History Questionnaire is administered following chemotherapy.

7.2.8 Exercise education session:

Participants randomized to the intervention will be oriented to the exercise intervention in person at their baseline cardiopulmonary exercise test before they receive intervention materials. Orientation will include instruction regarding the proper use of heart rate monitors, as well as how to warm-up, cool-down, stretch, proper footwear for injury prevention, aerobic exercise equipment safety, and completing the exercise logs. Those randomized into the exercise group will then be given three DVDs and their exercise intervention binder. The exercise physiologist will then provide ongoing support and monitoring of adherence in person at infusion sessions or via phone. The control group will also receive the same exercise education session as above following final exercise testing. Additionally, following surgical

resection and completion of all study visits DVDs and exercise binder will be given or shipped to the participant.

- 7.2.9 Breast tissue from biopsies/surgery**
H&E stained slides from diagnostic clinical pathology assessment will be viewed by a clinical pathology fellow and assessed for tumor infiltrating lymphocytes (TILs).

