6.2.1.2 Plan to destroy identifiers or a justification for retaining identifiers

We will identify eligible patients through electronic medical records prior to their consent in the study (pre-screen eligibility criteria). This information will be collected/retained on patients whom consent to be part of the study. No information from this screen will be collected/retained on patients whom do not consent to be part of the study.

6.2.2 Explanation for why the research could not practicably be conducted without access to and use of PHI

We will be conducting exercise testing and counseling (for those randomized to the intervention group) prior to starting chemotherapy. The timeline between recommendation for chemotherapy and initiation of chemotherapy is often short. Therefore, it is imperative we initiate recruitment for the study as soon as possible and thus schedule research visits on the same days as the patient comes to the Cancer Institute for testing related to their clinical treatment.

6.2.3 Explanation for why the research could not practicably be conducted without the waiver or alteration of authorization

Pre-screening individuals through electronic medical records allows for the timing of physician approval and approach of the patient. This study flow is being utilized to minimize patient burden for excess visits to the Cancer Institute for the research study.

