8.3 Statistical methods

Fisher's exact tests and χ^2 -tests will be used to examine between group differences in the overall proportion of patients experiencing treatment-related and training-related adverse events. A mixed-model repeated measures analysis of variance will be used to compare between group differences over time for outcome variables related to: cardiopulmonary fitness (VO₂max - stress testing), cardiac function (LVEF - echocardiogram), and tumor response (MRI). All efficacy outcomes will be assessed under the intention to treat principle. A two-sided significance level of 0.05 will be used for all statistical tests.

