14.0 Subject Stipend (Compensation) and/or Travel Reimbursements

Subjects in the control arm will receive DVDs and the exercise binder following the completion of final testing. Subjects in the intervention arm will receive DVDs and intervention materials (exercise binder and exercise logs) prior to starting chemotherapy. No other compensation will be given for time or travel.

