18.3 Subject Enrollment

Upenn – n=10

PSU – n=10 (between PSCI and Andrews Patel)

Eligible patients whom have consented to the study will be enrolled onto the study and the baseline exercise test will be conducted. The exercise test is conducted at HCAR at the HMC campus for PSCI and Andrews & Patel patients, and conducted at the Exercise Medicine Unit at Upenn for Upenn patients.

Following the baseline exercise test, the measurement technician whom conducted the exercise test will open the sealed envelope (labelled with the patient study ID#) that resides in each study binder. Each envelop contains the intervention group assignment for the respective study ID#. Thus, patients will be randomized following the exercise test. The randomization sequence was generated, assigned to patient ID#s, and envelops created, at study start up.

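### Section 7.2.7 places the first quality-of-life, fatigue and physical-activity surveys at the first infusion, after allocation is revealed, so the change comparison has no guaranteed pre-allocation baseline

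*Combined protocol and SAP*

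**What the plan says.** Section 7.2.7 lists the physical-activity, work-productivity, EQ-5D, SF-36, fatigue and adverse-effects surveys and sets their timing: "These will be administered during the first chemotherapy infusion session, a midpoint chemotherapy session (defined above for blood draws", with the third round at the last neoadjuvant session. It names no earlier round and no site.

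Allocation comes sooner. Section 18.3: "Following the baseline exercise test, the measurement technician whom conducted the exercise test will open the sealed envelope". Section 6.2.2 places this before treatment: "We will be conducting exercise testing and counseling (for those randomized to the intervention group) prior to starting chemotherapy". Section 7.2.8 adds: "Participants randomized to the intervention will be oriented to the exercise intervention in person at their baseline cardiopulmonary exercise test". Section 14.0 adds: "Subjects in the intervention arm will receive DVDs and intervention materials (exercise binder and exercise logs) prior to starting chemotherapy".

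For controls, section 7.2.6 asks for usual activity and no new exercise program, and provides attention contact: "Participants in the control group will be contact at each infusion session and asked about their experience and well-being during treatment". It does not say when a control woman is told her arm.

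Section 1.1 makes between-arm comparison of changes, including quality of life, the secondary aim. Section 8.3 reads "A mixed-model repeated measures analysis of variance will be used to compare between group differences over time for outcome variables related to" and then lists fitness, cardiac function and tumour response. Quality of life is not on that list.

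Section 16.1 has a table for University of Pennsylvania patients, introduced as showing where tests take place. It marks surveys and a blood draw for both arms in a pre-chemotherapy block and again in a final block. Its middle block holds only the exercise program and phone calls.

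**The concern.** A baseline for a randomized comparison of change should be recorded before anyone can react to the allocation. The plan does this for fitness, because the baseline exercise test precedes the envelope. Section 7.2.7 does not do it for the self-report measures, which are the outcomes most open to knowledge of the arm. By the first infusion one arm has been coached in exercise and holds its materials, while the other has been assigned to keep its usual activity. If that knowledge moves the answers, the first survey is already partly an outcome. A pre-allocation score that was never collected cannot be recovered in the analysis.

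At stake is the secondary comparison of changes in quality of life. In addition, staff at the University of Pennsylvania have two descriptions of the survey and blood-draw schedule to follow.

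**Working it through.** The plan's only power figure is the 80% in section 8.2. It reproduces and does not involve the surveys: difference 1.6 − 1.2 = 0.40 L/min; standard error √(0.35²/10 + 0.23²/10) = 0.132; ratio 0.40/0.132 = 3.02; two-sided Welch test at 0.05 with 15.6 degrees of freedom gives power of 80.8%.

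1. Order of events under 7.2.7. Written consent (5.1.1.1, 5.2.1), then the baseline exercise test, then the envelope (18.3), then orientation of the exercise arm at the same visit (7.2.8), with materials in hand before chemotherapy (14.0), then the first infusion with the first surveys (7.2.7). No single section states this order; it follows from reading them together. No section outside the 16.1 table gives an earlier survey.

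2. Number of women. Penn State 10 + University of Pennsylvania 10 = 20 (16.2, 18.3). If 7.2.7 governs every site, all 20 first surveys are post-allocation. If the 16.1 table governs its own site, the 10 Penn State first surveys are post-allocation. The other 10 are undetermined: the table puts them before chemotherapy, at the testing unit or at home, without placing them before or after the envelope.

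3. Effect of a shift. Let a be the between-arm difference in first-survey scores caused by knowing the allocation, and b the same at the last survey. A change score then carries b − a.
   - Shift at the first survey only (b = 0): the error is −a, the whole shift with its sign reversed. If the exercise arm scores better early, its benefit is understated.
   - Equal shift at both surveys (b = a): the error is 0.
   - Pre-allocation first survey (a = 0): the error is b, so any reporting shift at the last survey remains.

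   The documents give neither a nor b, and section 8.3 names no quality-of-life analysis. Neither the size nor the direction can be calculated.

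4. Schedule counts. Sections 7.2.2 and 7.2.7 give 3 blood draws and 3 survey rounds. The 16.1 table shows 2 and 2. The difference is the midpoint, for the site planned to enrol 10 of the 20.

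**The case against.** The strongest reply is that moving the survey is not shown to reduce bias. As step 3 shows, an open-label reporting shift that is equal at both surveys cancels in a change score when the first survey is post-allocation, and stays in full when it is pre-allocation. That is correct. A reader might infer that the plan biases the quality-of-life result in favour of exercise, or by a known amount; the documents support neither. What stands is that cancellation requires the shift at the first infusion to match the shift months later, and nothing in the plan supports relying on that. A pre-allocation score has a clear meaning without that assumption.

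The second reply concerns weight. Section 1.2 makes feasibility the only primary endpoint, section 1.3 marks secondary endpoints as not applicable, and section 8.3 does not name quality of life. This is a 20-woman pilot, and the 16.1 table places the exercise itself during chemotherapy, so exposure before the first survey is mainly knowledge and orientation. This stands and limits the rating. Quality of life is still in the stated secondary aim.

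Third, a reader might infer that all 20 women know their arm at the first survey. Orientation and materials document this for the exercise arm only; for controls the timing is not stated. The count of 20 is of surveys after the envelope, not of women shown to be aware.

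Fourth, a reader might infer from the 16.1 table that the University of Pennsylvania omits the midpoint or times its first and last surveys differently. The table is introduced as a list of locations, and its baseline and final blocks each include a draw taken in the infusion area. It may simply be abbreviated, so a different schedule is not proven.

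**Conclusion.** The point holds, as minor to moderate. Followed as written, section 7.2.7 collects no self-report score before allocation is revealed. This affects all 20 women, or 10 with a further 10 undetermined, depending on which section governs the University of Pennsylvania. The conclusion rests on the order of events in sections 18.3, 6.2.2, 7.2.8 and 14.0 and on no numerical assumption.

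No figure can be put on the bias, which depends on whether a shift persists to the last survey. A reader might also infer that the trial's main result is compromised. It is not: the feasibility endpoint, baseline VO₂, sample size and the 80% power do not depend on survey timing. The missing midpoint in the 16.1 table is a separate inconsistency of text and adds no weight to the allocation point.

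**What to change.** 1. In section 7.2.7, require the first surveys to be completed after written consent and before the envelope is opened, at every site. At Penn State both steps fall within the joint consent and baseline visit of section 5.1.1.1, and section 18.2 already provides REDCap delivery.

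   The cost is time. Using the 16.1 table's durations, assumed to apply at Penn State and excluding consent, the baseline visit goes from 45 to 45 + 30 = 75 minutes for controls, and from 45 + 60 = 105 to 135 minutes for the exercise arm. About 30 minutes come off the first infusion, and no visit is added. The burden is real, because section 6.2.2 warns: "The timeline between recommendation for chemotherapy and initiation of chemotherapy is often short". Enrolment and retention are also what the pilot is measuring.

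2. As a text edit only, align sections 7.2.2 and 7.2.7 with the 16.1 table so that one survey and blood-draw schedule applies at all sites. If the table is meant only to list locations, say so there.

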7.3 Duration of Participation

Estimated time to enroll all subjects = 12 months
Length of a participant's participation = 8 months

8.0 Subject Numbers and Statistical Plan

8.1 Number of Subjects

Enrolled: 20

8.2 Sample size determination

N=10 intervention
N=10 control

Our intervention protocol is adapted from Hornsby et al. They report a final VO₂ of 1.6 ± 0.35 L/min in the intervention group and 1.2 ± 0.23 L/min in the control group. Thus, we are powered at 80% to see the same difference in VO₂ with 10 people per group assuming unequal variances. We have powered off of VO₂ as it is our physiological measure of intervention success per physiological adaptation.

8.3 Statistical methods

Fisher's exact tests and χ^2 -tests will be used to examine between group differences in the overall proportion of patients experiencing treatment-related and training-related adverse events. A mixed-model repeated measures analysis of variance will be used to compare between group differences over time for outcome variables related to: cardiopulmonary fitness (VO₂max - stress testing), cardiac function (LVEF - echocardiogram), and tumor response (MRI). All efficacy outcomes will be assessed under the intention to treat principle. A two-sided significance level of 0.05 will be used for all statistical tests.

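### Background chemotherapy and the source of the final echocardiogram differ by HER2 status, but the LVEF and tumour-response comparison does not adjust for it, so a chance imbalance among 20 women can bias those secondary estimates

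*Combined protocol and SAP*

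**What the plan says.** - **Treatment.** Section 7.2.2 ties the midpoint blood draw to the end of anthracycline dosing for HER2- women on ACT, but sets it "at cycle 3 (HER2+ patients receiving TCH+pertuzumab". Women on at least two different background treatments are therefore compared together.
- **Regimen as a covariate.** Section 7.2.1 collects "treatment regimen (ACT, TAC, CAF), and medication use" among the clinical covariates. The list omits the TCH+pertuzumab group named in the next subsection, and no analysis uses the variable.
- **Echocardiogram.** Section 7.2.3 says "Resting echocardiograms are not obtained clinically following chemotherapy for HER2- patients; therefore this measurement is additional for research". HER2+ women have theirs in clinical care. The footnote to the University of Pennsylvania table in 16.1 likewise limits the research echocardiogram to women not treated with trastuzumab.
- **Allocation.** Section 7.1 describes a computer-generated sequence. Section 18.3 adds: "The randomization sequence was generated, assigned to patient ID#s, and envelops created, at study start up". Neither section mentions a stratification factor.
- **Analysis.** Section 8.3 says: "A mixed-model repeated measures analysis of variance will be used to compare between group differences over time for outcome variables related to: cardiopulmonary fitness", and the same sentence goes on to LVEF and MRI tumour response. The model has no term for HER2 status or regimen. "A two-sided significance level of 0.05 will be used for all statistical tests".
- **Status of these outcomes.** The primary endpoint (1.2) is feasibility. LVEF and tumour response belong to the secondary aim in 1.1.

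**The concern.** HER2 status determines which drugs a woman receives and where her final LVEF measurement comes from. The background section calls chemotherapy cardiotoxic, and section 12.2 looks to exercise for gains in cardiac function and tumour response. If regimen affects those outcomes and the arms differ in their share of HER2+ women, the arm estimate mixes exercise with drugs.

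The repeated-measures structure does not remove this. Regimen acts after baseline, so it affects the change itself, and the group-by-time contrast carries the imbalance. When the arms happen to balance, the regimen difference stays in the error term instead. At stake is how far the secondary estimates from a 20-woman trial can be trusted.

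**Working it through.** **The plan's own figure.** Section 8.2 takes from the cited phase II trial a "final VO₂ of 1.6 ± 0.35 L/min in the intervention group and 1.2 ± 0.23 L/min in the control group" and concludes that "we are powered at 80% to see the same difference in VO₂ with 10 people per group assuming unequal variances". Check with the Welch t-test:

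- SE = √(0.35²/10 + 0.23²/10) = √0.01754 = 0.1324.
- Noncentrality = 0.4/0.1324 = 3.02; Satterthwaite df = 15.6.
- Power = 80.8% (80.5% by simulation).

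The stated 80% reproduces. It concerns VO₂ only; the plan gives no power for LVEF or tumour response.

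**Inputs the documents do not give.** These are assumptions, shown over a range: the number K of HER2+ women among 20 (4 to 10), and the effect g of regimen on change (0.5, 1.0 or 1.5 residual SD). Allocation is taken as exactly 10:10.

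**Step 1: how often the arms differ.** The HER2+ count in one arm is hypergeometric. For K = 6:

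- P(3-3) = C(6,3)·C(14,7)/C(20,10) = 20 × 3432/184756 = 0.372, so P(4-2 or worse) = 0.628.
- P(5-1 or worse) = 2 × (6 × 2002 + 1001)/184756 = 0.141, counting both directions.

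| K | Gap of at least 2 women | Gap of at least 4 women |
|---|---|---|
| 4 | 58% | 9% |
| 5 | 30% (gap is 3 or more) | 3% (gap is 5) |
| 6 | 63% | 14% |
| 7 | 35% (gap is 3 or more) | 6% (gap is 5 or more) |
| 8 | 65% | 17% |
| 10 | 66% | 18% |

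For odd K the gap is always odd, so a gap of one is the best attainable and the next is three. If K is random, each woman having a 20-50% chance of being HER2+, a gap of at least two has probability 39-50% and of at least four 5-12%.

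**Step 2: conditional bias.** With a HER2+ women in one arm and b in the other, bias = (a/10 − b/10) × g.

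- 4-2: 0.2 × g = 0.10, 0.20, 0.30 SD.
- 5-1: 0.4 × g = 0.20, 0.40, 0.60 SD.

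**Step 3: type I error of the unadjusted comparison of change** (100,000 simulated trials per scenario, K = 6):

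| Split | g = 0.5 | g = 1.0 | g = 1.5 |
|---|---|---|---|
| 3-3 | 4.3% | 3.2% | 1.7% |
| 4-2 | 4.9% | 4.9% | 4.3% |
| 5-1 | 6.6% | 10.2% | 14.6% |
| All splits, weighted by probability | 5.0% | 5.0% | 5.0% |

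With K = 7, a 5-2 split gives 5.5%, 6.6% and 7.6%. With HER2 status in the model, bias is about zero and type I error 4.9-5.1% at every split tested, with 17 instead of 18 degrees of freedom.

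**Step 4: precision.** At 3-3 the unadjusted error variance rises by 2 × 10 × 0.3 × 0.7 × g²/18 = 0.233 g², which is 6%, 23% and 53%. The reported standard error is then about 3%, 11% and 23% too large (square roots of 1.058, 1.233 and 1.525).

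Adjustment has its own price when arm and HER2 status are correlated. At 5-1, r² = (5 × 9 − 5 × 1)²/(10 × 10 × 6 × 14) = 1600/8400 = 0.190, so the standard error grows by √(1/0.810) = 1.11. At 4-2, r² = 400/8400 = 0.048 and the factor is 1.02. If regimen has no effect, that increase buys nothing.

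**The case against.** The strongest reply is that randomisation already protects the comparison. Averaged over all allocations the unadjusted test rejects 5% of the time, and at the common 4-2 split it rejects no more than that. Clear inflation needs a gap of about four women, which is uncommon and can fall in either direction. These are secondary outcomes of a feasibility trial. All of this stands, and it limits the point to bias in the estimate from the allocation that actually occurs, plus precision.

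A reader might infer more in several places where the documents do not support it:

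- **That regimen is known to change tumour response.** No section says so, and cardiotoxicity is described only in general terms. A difference in response rates would not fit in any case, because 8.3 puts MRI tumour response in a repeated-measures model and defines no response rate.
- **That HER2+ women have the final echocardiogram at a different time point.** Section 7.2.3 sets baseline and post-chemotherapy measurements for everyone. What differs is the source, and that varies by HER2 status, not by arm, so it reaches the comparison only through the same imbalance.
- **That the different midpoint triggers matter here.** They govern blood draws and surveys, not LVEF or MRI.
- **That TCH+pertuzumab cannot be recorded.** Section 7.2.1 gives a list in prose, not a closed field. It is incomplete against 7.2.2 and the two need reconciling, but it does not prove that data will be lost.

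**Conclusion.** The point holds as one about conditional bias and precision in the LVEF and tumour-response estimates. It does not show that the unadjusted test is invalid. One might read it as saying that a likely imbalance will pass for an exercise effect. The figures do not support that: the likely imbalance does not raise the false-positive rate, and the imbalance that does raise it is unlikely (5-1 or worse has probability 14% with 6 HER2+ women). Nor is every arm difference partly a drug difference, since at 3-3, probability 37% with K = 6, regimen adds nothing to it.

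The sizes rest on 10:10 allocation, an assumed HER2+ count and an assumed regimen effect. If regimen does not affect these outcomes, there is no bias. The feasibility conclusion does not depend on any of this. The change is still worth making, because HER2 status is a baseline factor that allocation cannot alter, and choosing the adjustment after seeing results by arm would look selective.

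**What to change.** - In 8.3, pre-specify baseline HER2 status (HER2+ versus HER2-) and its interaction with time as fixed effects in the LVEF and tumour-response models. The interaction is essential: with measurements at two time points and complete data, a HER2 main effect alone leaves the group-by-time contrast unchanged.
- Use HER2 status as established before randomisation, not the regimen later received. A woman on a regimen outside the listed ones then still has a place in the model.
- Report HER2 status and regimen by arm. Give both outcomes by arm within HER2 status descriptively only, because with 6 HER2+ women a cell may hold as few as one to three.
- Complete the regimen list in 7.2.1 so that it covers the TCH+pertuzumab group in 7.2.2.
- Leave the allocation envelopes unchanged. The sequence was fixed at start-up.

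The cost is one or two degrees of freedom and, if regimen turns out not to matter, a slightly wider interval when the arms are imbalanced. No visit, procedure or sample-size change is needed.
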